## **DATA AND SPECIMEN BANKING**

Data will initially be entered onto case report forms and then into the Research Electronic Data Capture (REDCap) database. All questionnaires will be electronic (created or copied into REDCap) and completed by the participant via links sent to his/her email address. Once completed, the questionnaire data are stored in the REDCap database and cannot be altered by any team members. This process will be designed so that the system automatically sends the correct questionnaires at defined intervals and tracks participants over the follow-up, informing research staff either when participants have completed the battery or when they have gone outside the allotted time window and must be called. Thus, REDCap will aid in the promotion of scheduled and diligent contact between participants and the research team. All remaining data will be collected by the designated clinical manager as well as by the MRI research team. Scanning data will all be digital and burned onto DVDs, sent to a Northwestern University archive system, and stored in the lab's secure servers. Likewise, data collected with our smartphone app will be digitally stored in the lab's secure server. Only subjects' participation identification numbers (PIPs) will be included in any of these materials; a master study list will be maintained by the lead clinical investigator ([name]). Access to this list will be limited to the site investigators, clinical coordinator, and other study personnel directly involved with data collection on an as needed basis. All the data will be collected specifically for this study and not in the course of usual clinical care. All non-digital data (e.g., consent forms) will be stored in a locked cabinet in a locked room. Any digital information will be pass-word protected and if any of this has identifying information on it, it will be encrypted.

### **Access to PHI:**

All data collected will be linked to participants by their unique study participation identification numbers (PIPs), provided at the time of screening. A master study list linking participants' names to study identification numbers will be the only means of linking data to specific individuals. This list will be kept on an encrypted personal computer residing in the [name] lab, not connected to the internet, and with password protection. Only [name] and [name] will have access to this file, and it will only be used in case of an unforeseen emergency need.

## **SHARING RESULTS WITH PARTICIPANTS**

Screening laboratory tests may be shared with the participants and/or their physicians at their request. The results of the questionnaires and brain scans will not be provided to the participants.

## **STUDY TIMELINES**

Participants may be involved for approximately 7 weeks; for a total of 11 visits. Each treatment period will consist of five consecutive days of stimulation sessions followed by two weeks wash

STU#:

out period. It is anticipated that enrollment will require approximately 8 months. The primary analyses will be completed 6 months later.

## INCLUSION AND EXCLUSION CRITERIA

Pre-screening of participants will occur by phone or email. We will discuss the study aims and objectives, the procedures that will need to be followed, and the risks and potential benefits with all individuals during pre-screening procedure. A written consent form will be provided to each subject prior to any procedures being carried out; this will be read by the potential subject and any and all questions answered by the coordinator and/or site investigator. Subject will sign two copies of the consent form; one will be given to the subject and one will be kept in the subject's file.

### Inclusion Criteria:

- ≥ 6 months of back pain on a daily basis;
- male or female with no racial or ethnic restrictions;
- 18 to 75 years old;
- average back pain intensity > 4/10 at study entry;
- must be able to read, understand, and sign consent form;
- generally healthy.

### Exclusion Criteria:

- back pain with fever, chills, rheumatoid arthritis, ankylosing spondylitis, acute vertebral fractures,
- history of tumor in the back;
- back surgery within the past 6 months;
- Chronic neurologic conditions, e.g., Parkinson's
- involvement in litigation regarding back pain;
- other severe medical diseases;
- pregnancy;
- positive urinary screen for any recreational drugs,
- opioids use;
- use of anticoagulants (low dose ASA allowed);
- history of gastric ulcer; renal insufficiency or congestive heart failure,
- contraindication to MRI,
- contraindication to TMS; including history of seizure/epilepsy\*
- Any medical condition that in the investigator's judgment may prevent the individual from completing the study or put the individual at undue risk;
- In the judgment of the investigator, unable or unwilling to follow protocol and instructions;
- Diagnosis of major depression;
- Intra-axial implants (e.g. spinal cord stimulators or pumps)

\* contraindication to TMS such as: history of seizures, unexplained loss of consciousness, any metal implants in the head, frequent or severe headaches or neck pain, any other electronic implanted medical devices such as pacemakers, defibrillators, or implant medication pump.

## VULNERABLE POPULATIONS: NONE

## PARTICIPANT POPULATION(S)

Accrual Number:	Category/Group: (Adults/Children)	Consented: Maximum Number to be	Enrolled: Number to Complete
-----------------	--------------------------------------	------------------------------------	---------------------------------

STU#:

	Special/Vulnerable Populations)	Consented or Reviewed/Collected/Screened	the Study or Needed to Address the Research Question
Local	16	16	16
Study-wide	16	16	16
Total:	16	16	16

## RECRUITMENT METHODS

Potential patients will be screened via a database maintained by one of the co-investigators ([name]), the registry is approved under the IRB (STU00007522 - Protocol title: Physical Medicine & Rehabilitation Registry). We will also extend recruitment through community and partnerships with medical institutions (Northwestern Medicine, Shirley Ryan AbilityLab), through online advertisement, and by flyer-based methods including ads.

Materials that will be used to recruit subjects will be uploaded in the IRB application, and only used once they have been approved. They include ads, brochures, and letters. Contact information on the fliers/ads and other subject facing recruitment materials will be updated as needed without IRB approval. No other content on the subject facing recruitment materials will be changed without IRB approval, only contact information.

## COMPENSATION FOR PARTICIPATION IN RESEARCH ACTIVITIES

Participants will not be paid at the time of prescreening. For the screening visit, participants will receive \$75 (\$25 for questionnaires + \$40 for the MRI) for travel and their involvement. For visits after the screening period (V2-V11) participant will receive \$20/stimulation session; \$100 dollars will be reloaded at the PNC card after each stimulation round (5 visits). Participants will receive \$40 dollars for each MRI completed. Participants will receive \$0.25 per eDiary entry recorded throughout the study, ratings are capped at a max of 2/day and as the study lasts approximately 7 weeks. In addition, participants will receive an extra \$20 if complete all the study visits and bonus of \$20 dollars if they complete more than 90% of the pain diary ratings (90% is approximately 90 rates). In all visits, participants can opt to receive a parking voucher. If a parking voucher is required for one of the Northwestern Parking garages, \$6 will be deducted from total visit payment. Payment may be prorated based on visit completion. All compensation will be made using a Stored Value Card (VISA).

Visit	Number of Visits	Amount per visit	Total Amount	Payment Type
Screening/MRI completion	1	\$75	\$75	PNC card
V2-V11	10	\$20	\$200 + \$20 	PNC card
Second MRI completion	1	\$40	\$40	PNC card
PainApp ratings	100	\$0.25 dollar/response, 2 times per day maximum + \$20 	\$25 + \$20 	PNC card

STU#:

 Participants will receive an extra \$20 if complete all the study visits, including 10 stimulation visits.

If participants complete 90% of all pain diaries entries (around 90 entries) they will receive an additional \$20 dollars at the end of the study.

## WITHDRAWAL OF PARTICIPANTS

Participants may be withdrawn from the study if they are not able to undergo brain MR imaging or if they do not provide regular pain data with the cellphone app. Participants will be notified that they will have to discontinue the study if those circumstances occur.

If a participant withdraws early, payment will be made for the portion of the research study that has been completed (prorated to the nearest 1-hour increment). Incomplete data sets obtained from participants (due to early withdrawal) will be excluded from the primary analysis and included in an exploratory full dataset analysis.

## RISKS TO PARTICIPANTS

### Taking part in this study may involve the following risks:

The most common side effects of rTMS can include mild headaches or discomfort at the stimulation site. This occurs in approximately 5% of subjects. The subject is allowed to stop the stimulation at any time if they feel uncomfortable. These effects generally wear off shortly after the session and can be treated via over-the-counter analgesics. If subjects experience discomfort at a stimulation location, research staff will attempt to move the stimulator to a location that minimizes this discomfort. Research staff will be in constant contact with the subject during the rTMS procedure and will discontinue the protocol if discomfort cannot be successfully reduced. Vital signs will be collected and used to exclude subjects from rTMS if outside of normal established ranges (see above). With the permission of the subject, the primary care physician will be contacted by the research team to arrange follow-up care if vital signs are outside of the normal range.

Although extremely rare, undergoing rTMS may induce a seizure. The risk of seizure due to rTMS is extremely rare with the rTMS procedures that will be used under this protocol. The screening procedures and rTMS stimulation protocol used here is in accordance with recommendations by the safety of TMS consensus group and by the international workshop on the safety of repetitive TMS, and the proposed rTMS procedures are classified as very low in risk based on these recommendations. The risk of seizure for our rTMS parameters among individuals meeting our safety requirements (including no history of seizure/epilepsy, among other exclusionary criteria) is quantified in two publications: Rossi et al. (2009) and Oberman et al. (2011). Rossi et al. Identified one instance of seizure among all studies conducted from 1998-2008 among subjects with no history of seizure meeting our inclusion/exclusion criteria. There were additional instances of seizure reported among subjects who would be excluded from our studies because of psychiatric diagnoses, current use of anti-psychotic drugs, and neurological diagnosis, all of which are exclusionary for our studies. The risk estimate quantified from Rossi et al., 2009, for subjects meeting our criteria is 0.01% likelihood of seizure during a rTMS session. Oberman, 2011, reviewed studies using the same inclusion/exclusion criteria as in our studies and report a risk of 0.02% likelihood of seizure during a rTMS session. The risk of seizure for an individual with no seizure history and meeting our other inclusion/exclusion criteria is therefore approximately 0.01-0.02% (~1 to 2 in 10,000).

Despite the very low risk of seizure for these procedures, trained clinical staff (nurse, doctor, nurse practitioner or a physician assistant) will be present for all rTMS sessions. Trained clinical

STU#:

## **POTENTIAL BENEFITS TO PARTICIPANTS**

We cannot promise any benefits; however, possible benefits include a decrease in pain as a result of the stimulation sessions. We are not able to estimate at this time the probability, magnitude or duration of benefit. We hope to define these parameters with the results of this study.

## **DATA MANAGEMENT AND CONFIDENTIALITY**

Data will initially be entered onto case report forms and then into the Research Electronic Data Capture (REDCap) database. All questionnaires will be electronic (created or copied into REDCap) and completed by the participant via links sent to his/her email address. Once completed, the questionnaire data are stored in the REDCap database and cannot be altered by any team members. This process will be designed so that the system automatically sends the correct questionnaires at defined intervals and tracks participants over the follow-up, informing research staff either when participants have completed the battery or when they have gone outside the allotted time window and must be called. Thus, REDCap will aid in the promotion of scheduled and diligent contact between participants and the research team. All remaining data will be collected by the designated clinical manager as well as by the MRI research team. Scanning data will all be digital and is burned onto DVDs, sent to a Northwestern University archive system, and stored in the lab's secure servers. Likewise, data collected with our smartphone app will be digitally stored in the lab's secure server. Only subjects' participation

STU#:

identification numbers (PIPs) will be included in any of these materials; a master study list will be maintained by the lead clinical investigator ([name]). Access to this list will be limited to the site investigators, clinical coordinator, and other study personnel directly involved with data collection on an as needed basis. All the data will be collected specifically for this study and not in the course of usual clinical care. All non-digital data (e.g., consent forms) will be stored in a locked cabinet in a locked room. Any digital information will be pass-word protected and if any of this has identifying information on it, it will be encrypted.

### **Data Analysis Plan**

MRI data will be analyzed using the FSL software library [30]. Briefly, structural data will be skull-stripped and normalized to MNI space through nonlinear transformation. Functional data will be motion corrected and smoothed with a 4 mm smoothing kernel. Data will be further denoised by performing motion-censoring and regressing out the motion parameters. Finally, data will be band-pass filtered (0.01 to 0.1 Hz). Functional connectivity analyses will be carried on by performing Pearson correlations between the BOLD time series of a hippocampal seed and all other voxels in the brain. The maximal statistically significant cluster near a predetermined coordinate in the parietal cortex (see Wang et al. 2014) will be extracted, spatially warped to the subject native space, and fed into the TMS neuronavigation system for stimulation.

Statistical analyses will be performed using the software R. We use repeated-measures within-subject analysis of variance for dependent variables 1) change in painApp immediately after rTMS relative to baseline, and 2) for change in painApp in the long term (average over the second week after rTMS) relative to baseline, with independent factors being hippocampus-rTMS and sham-rTMS; with Bonferroni post-hoc comparisons. If the ANOVAs are significant and post-hoc comparisons indicate superiority of hippocampus-rTMS, we declare that the approach is a clinically important means of pain control in CBP, and newer larger studies should be launched.

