## **STUDY ENDPOINTS**

This is a mechanistic study; therefore, the main study aim is to show that the hippocampal stimulation leads to functional connectivity changes across series of hippocampal networks and how these connectivity changes are correlated with pain decrease.

The secondary outcome will be changes in pain ratings. The effects of the brain stimulation will be measured by daily pain ratings (painApp) and questionnaires, using our in-house pain app. As we collect these outcomes repeatedly, we will have changes in pain immediately after the stimulation session and also over the next 2-weeks. We will test immediate and 2-weeks changes in painApp ratings relative to baseline. Questionnaire analyses, and other time course analyses of painApp data will be treated as exploratory in nature.

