### **MRI Scan:**

Subjects will undergo MRI scanning at the Northwestern University, Department of Radiology Center for Translational Imaging (CTI). All procedures are standard in our laboratory and have been approved in multiple previous IRB protocols.

More specifically, we will conduct a MRI scan (Siemens Trio, 3T, 64-channel head coil) with both structural (T1 scan, 5 minutes) and rsfMRI (EPI scan, 8 minutes) protocols. No contrast will be used in the MRI.

The structural scan will allow us to use the built-in neuronavigation TMS system, for optimal localization of the stimulation sites. Resting-state fMRI will be used to identify the functional localization for indirect stimulation of the hippocampus. To do so, we will follow a well-established in-house processing pipeline, replicating the methods used in our previous experiments using this method . Briefly, whole-brain seed-based correlation will be performed, using the left dorsal hippocampus as a seed region. This will allow us to identify, at a single-subject level, the exact parietal target that has maximal connectivity to the dorsal hippocampus. By stimulating this parietal target, modulation of the hippocampus connectivity can be achieved non-invasively  and with long-lasting effects in brain connectivity after three stimulation sessions .

In this same visit, participants will further complete questionnaires regarding pain ratings and the characteristics of their pain (see below for detail information).

Participants will be assigned to one of the six possible stimulation sequences and trained on our pain app (a smartphone-based tool used to rate pain and mood on NRS scales, as well as indicate rescue medication use, twice a day). They will be asked to use the pain app for the next 7-10 days prior to the first round of intervention and during all the study duration.

STU#:

There will be 2 MRI visits: one at baseline (visit 1), the second MRI will depend on participants allocation: participants randomized to group 1 will have a second MRI at visit 6; and participants randomized to group 2 at visit 11.

- **Visit 2 – 11** (Approx Time: 1 hour)

Intervention visits: These visits will be scheduled ~1 week after the visit 1 measurements are done.

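### Motion weights are fitted on unfiltered data and the band-pass comes last, so in-band motion is mis-corrected if motion affects the signal differently at faster frequencies

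*Combined protocol and SAP*

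**What the plan says.** The Data Analysis Plan lists the steps in order. First, "Functional data will be motion corrected and smoothed with a 4 mm smoothing kernel". Next, the data are denoised by "motion-censoring and regressing out the motion parameters. Finally, data will be band-pass filtered (0.01 to 0.1 Hz"). Connectivity is then obtained by "performing Pearson correlations between the BOLD time series of a hippocampal seed and all other voxels in the brain". The section does not say whether the motion parameters are filtered too, or whether regression and filtering share one model. It also does not say how censored frames pass through the filter. It gives no repetition time, no number of motion parameters and no censoring threshold.

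The MRI Scan section sets the length: "rsfMRI (EPI scan, 8 minutes) protocols". It plans two scans per participant, one at visit 1 and one at visit 6 or 11 depending on group. Connectivity from the first scan also selects each participant's parietal stimulation target. Under Study Endpoints, "the main study aim is to show that the hippocampal stimulation leads to functional connectivity changes across series of hippocampal networks", together with how those changes correlate with pain decrease.

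**The concern.** The motion regression and the connectivity measure work on different frequency content. Least squares on unfiltered data gives one weight per motion trace, averaged over slow and fast movement according to their variances. After filtering, only the slow part matters, and the averaged weight may be wrong for it. One example is a fast part of the trace that is mostly estimation noise or apparent motion with little effect on BOLD. The weight is then pulled towards zero and some slow motion artefact stays in the data. If the fast part has the stronger effect, the weight is too large and slow motion is over-corrected. In both cases seed and voxel share the remainder, which appears as positive correlation.

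The measure affected carries the main aim and guides targeting. Averaging is limited: two scans per participant and a final sample of 12 (Power Calculation). The Risks to Participants section says pain may worsen while a participant lies in the scanner. It is therefore plausible, though not shown, that movement tracks pain, and leftover motion could then resemble the connectivity-pain link under study.

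**Working it through.** The plan states no figure on this point, so there is none to reproduce.

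**Inputs from the documents:** step order, 0.01-0.1 Hz band, 8-minute scan.

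**Assumed inputs:** repetition time 2 s (480/2 = 240 frames); 6 motion traces; 12 censored frames (5%); true correlation 0; the same motion artefact in both voxels; h, the fast-to-in-band variance ratio of the traces, 0.5 to 1; v, in-band motion variance as a share of in-band neural variance, 0.2 to 1.

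**Formula.** Let bL and bH be the motion-to-BOLD coupling in the band and above it, with in-band trace variance 1, so bL = √v. The full-band weight is (bL + h·bH)/(1 + h). The in-band coefficient left after filtering is

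d = bL − (bL + h·bH)/(1 + h) = (bL − bH)·h/(1 + h),

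and with neural variance 1 the false correlation is about r = d²/(1 + d²).

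Example with v = 1, h = 1, bH = 0: d = 0.5 and r = 0.25/1.25 = 0.20. With bH = bL, d = 0 for any h. With bH = 2bL, d changes sign (over-correction) but r is the same as for bH = 0.

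| v | h | r, bH = 0 or 2bL | r, bH = 0.5bL | r, bH = bL |
|---|---|---|---|---|
| 0.2 | 0.5 | 0.022 | 0.006 | 0 |
| 0.2 | 1 | 0.048 | 0.012 | 0 |
| 0.5 | 0.5 | 0.053 | 0.014 | 0 |
| 0.5 | 1 | 0.111 | 0.030 | 0 |
| 1 | 0.5 | 0.100 | 0.027 | 0 |
| 1 | 1 | 0.200 | 0.059 | 0 |

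**Simulation** (400 runs per setting, 12 spiked and censored frames). Mean r under the planned order was 0.03-0.20 for bH = 0, 0.02-0.19 for bH = 2bL, 0.00-0.06 for bH = 0.5bL, and −0.01 to 0.01 for equal coupling. One joint model gave −0.02 to 0.01 throughout. For scale, the SD of r from a single scan under the planned order was 0.09-0.12.

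**Change between scans.** With no true change and equal motion at both scans, the offsets cancel: 0.111 − 0.111 = 0. If v rose from 0.2 to 0.5 with h = 1 and bH = 0, the false change would be 0.111 − 0.048 = 0.063.

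**Precision of the joint model.** The frequency step is 1/480 Hz, so the band holds bins 5 to 48: 44 bins, or 88 degrees of freedom. The remaining 240 − 88 = 152 go to the filter terms. With 6 motion terms and 12 spike terms, 240 − 152 − 6 − 12 = 70 remain, and the SD of r is about 1/√70 = 0.12. With 20% of frames censored (48), 240 − 152 − 6 − 48 = 34 remain, and the SD is about 1/√34 = 0.17. Simulation gave 0.16-0.18, against about 0.12-0.13 for the planned order.

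**The case against.** A reader might infer that any fast movement in the traces causes under-correction. It does not: with equal coupling the planned order removed in-band motion completely, and with unequal coupling the error can go either way.

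A reader might also infer that the main endpoint is biased. The calculation concerns one scan. An equal offset at both scans cancels when nothing has truly changed, and the documents do not show that motion differs between scans or follows pain. Nor is a displaced stimulation target shown. The plan takes the maximal cluster near a predetermined coordinate, and an artefact shared equally by all voxels need not move the peak.

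The size rests almost wholly on assumptions. The top values need motion variance as large as neural variance after realignment, and fast motion with no coupling or double coupling. At half coupling, r is at most about 0.06.

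The text is introduced as a brief account, and the MRI Scan section points to an established in-house pipeline that replicates earlier work. The regressors may be filtered, and censoring may be done by spike regressors or interpolation. It cannot be said that the filter runs across deleted or zeroed frames.

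Finally, the planned order is not the worst sequential choice. Filtering the data first and regressing on unfiltered traces left r of 0.25, 0.33 and 0.42 at h = 0.5, 1 and 3, with equal coupling and v = 1.

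All of this stands, and it limits the point to a conditional one. It does not remove it: the written order relies on equal coupling across frequencies without saying so, and a joint model does not need that assumption.

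**Conclusion.** The point holds in conditional form. As written, in-band motion is mis-corrected when the motion traces contain fast movement and its coupling to BOLD differs from the in-band coupling. Under the assumed ranges the false single-scan r lies between about 0 and 0.2, with zero a genuine possibility. Of the inputs that set the size, only the scan length is in the documents. Carry-over to the connectivity change, or to its correlation with pain, further requires motion to differ between scans or to track pain. This is a low-cost improvement to the measure behind the main aim and the target map. It is not a proven bias in either.

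**What to change.** In the Data Analysis Plan, replace the sequence with one regression per scan. It should contain the motion parameters, one spike regressor per censored frame, and the sine and cosine terms outside 0.01-0.1 Hz. Compute the Pearson correlation on the uncensored residual frames. An acceptable alternative is to interpolate censored frames, filter data and motion traces identically, and then regress. Use the same model for the visit 1 target map and for both scans in the change analysis, and state the number of motion parameters, the censoring threshold and the repetition time. If the in-house pipeline already does this, one sentence saying so is enough.

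The cost is a script change and a short text edit, with no new data. There are two downsides. Changing the target map may depart from the pipeline the study says it replicates. Heavily censored scans also lose precision: at 20% of frames censored, the SD of r is about 0.17 against 0.13. At 5% censored the loss is slight (about 0.12 against 0.11). The number of censored frames per scan should therefore be reported.

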Parameters will be identical to the hippocampus-stimulation, except that the coil will be flipped over to the sham side and a stimulating electrode will be attached to the skin near the parietal rTMS target location. This electrode will be used to deliver a small current mimicking real stimulation sensation, therefore participants cannot reliably discriminate physical sensations for real versus sham rTMS.

A trained co-investigator on the study will administer the rTMS. Prior to performing any study procedures, the study staff member will be trained in the techniques of rTMS as well as all aspects of the evaluations. This study staff member will then be evaluated by the PI of the study. The PI will then give confirmation that the co-investigator is qualified to administer the stimulation and the evaluations. Subjects are allowed to miss up to 1 stimulation visit in each treatment round, we will drop out subjects that miss more than 1 stim visit per round.

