#### **Stimulation modality sequences:**

The order of the stimulation modalities will be different across subjects. Subjects will be randomly assigned to one of two possible groups/stimulation sequences (fig 1). Before enrollment starts, we will produce 18 envelopes containing the stimulation sequence (see below possible combinations; we expect to use only 16). The stimulation sequence will be kept in sealed envelopes; therefore, subjects will get their assignment according to the order of entrance in the study. The study coordinator will retain the original sequence list which will be kept in a locked place. The study staff who provides the stimulation TMS session will be the only un-ed personnel.

STU#:

[figure not shown]

Figure 1: Study design and stimulation sequence. The subjects will be allocated to 1 envelop according to the entrance in the study. All participants will receive all the 2modalities of stimulation. Each round is composed by 5 daily session of stimulation, participants will not know which round is active and which is sham. Participants randomized to group 1 will have a second MRI at visit 6; and participants randomized to group 2 at visit 11.

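### The crossover pain analysis has no round (period) term: if pain shifts between rounds, power is lost when the sequences are equal and the estimate is biased, in either direction, when they are not

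*Combined protocol and SAP*

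**What the plan says.** Under Stimulation modality sequences, "Subjects will be randomly assigned to one of two possible groups/stimulation sequences". The text on Visits 2–11 gives everyone both conditions, five daily sessions per round, with a two-week washout between rounds.

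The Data Analysis Plan contains the only statistical model. It is a within-subject repeated-measures ANOVA on two outcomes, "change in painApp immediately after rTMS relative to baseline" and the longer-term change ("average over the second week after rTMS"), "with independent factors being hippocampus-rTMS and sham-rTMS; with Bonferroni post-hoc comparisons". If the ANOVAs are significant and favour hippocampal stimulation, "we declare that the approach is a clinically important means of pain control in CBP", and larger studies are to follow.

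No round, period, order or sequence term appears anywhere. Study Endpoints says "We will test immediate and 2-weeks changes in painApp ratings relative to baseline". Neither section says whether baseline is one value before round 1 or is taken again before each round. The only baseline rating period described precedes round 1: "They will be asked to use the pain app for the next 7-10 days prior to the first round of intervention".

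**The concern.** With two conditions and no other factor, the ANOVA is a paired t-test on each participant's hippocampus-minus-sham difference. Any general change in pain between rounds enters that difference with opposite signs in the two sequences. It then adds to the error variance and, if the sequences are unequal, moves the estimate.

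Whether it matters depends on the undefined baseline. A single baseline cancels in the within-person comparison, so the whole shift stays. A fresh baseline before each round cancels a pure level shift and leaves only drift that differs between rounds.

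Equal sequences among completers are not assured. The text states no split for the 18 envelopes, of which 16 are expected to be used (Figure 1 is not shown). During the rounds, "we will drop out subjects that miss more than 1 stim visit per round", and Withdrawal of Participants removes incomplete participants from the primary analysis.

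At stake is a claim of clinical importance, and the launch of larger studies, both tied to these tests.

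**Working it through.** **The plan's own figure.** Power Calculation gives 12 completers from 16 recruited, with no SD, effect, alpha or power. The 12 cannot be reproduced. The two numbers imply only a 4/16 = 25% loss.

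**Set-up.** Let τ be the effect (hippocampus minus sham), δ the round 2 minus round 1 shift that survives baseline, and SD that of the within-person difference d. Let nH be the number hippocampus-first, nS the number sham-first, and N = nH + nS = 12.

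- Mean of d: τ − δ if hippocampus-first, τ + δ if sham-first.
- Without a round term, the estimate has mean τ + δ(nS − nH)/N. The bias is 0 at 6:6, δ × 2/12 = one sixth of the shift at 7:5, and δ × 4/12 = one third at 8:4.
- Without a round term, the expected variance of d is SD² + 4δ²nHnS/[N(N − 1)]. At 6:6 with δ = SD = 1 this is 1 + 144/132 = 2.09, about double.
- With a round term, the estimate is unbiased with SE = (SD/2)√(1/nH + 1/nS) on 10 df, whatever the shift.

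**Assumptions not in the documents.** Two-sided 5% level; τ = −1 NRS point; pain falls between rounds and the whole fall survives baseline; no carryover. Figures are per ANOVA. The averages assume 12 completers drawn at random from a 9:9 envelope set, which gives 6:6 with probability 38%, 7:5 49%, and 8:4 or worse 13% (6.6% in each direction). The chance of a split other than 6:6 is therefore 62%; it is about 57% from 8:8 randomised and 77% under simple randomisation.

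| SD, fall | Fall/SD | Power at 6:6, without / with term | Type I at 6:6, without | Averaged power, without / with | Averaged type I, without |
|---|---|---|---|---|---|
| 1, 1 | 1.00 | 0.62 / 0.88 | 0.006 | 0.61 / 0.87 | 0.017 |
| 1.5, 1 | 0.67 | 0.39 / 0.55 | 0.020 | 0.40 / 0.54 | 0.029 |
| 1.5, 0.5 | 0.33 | 0.51 / 0.55 | 0.040 | 0.51 / 0.54 | 0.043 |
| 2, 0.5 | 0.25 | 0.33 / 0.35 | 0.044 | 0.33 / 0.34 | 0.046 |

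**Unequal splits, no round term.** The last two columns give errors favouring hippocampal stimulation when sham-first is the larger sequence, against 0.025 nominal.

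| SD, fall | Two-sided type I, 7:5 | Two-sided type I, 8:4 | Favouring hippocampus, 7:5 | Favouring hippocampus, 8:4 |
|---|---|---|---|---|
| 1, 1 | 0.015 | 0.051 | 0.014 | 0.051 |
| 1.5, 1 | 0.028 | 0.056 | 0.024 | 0.055 |
| 1.5, 0.5 | 0.043 | 0.053 | 0.030 | 0.045 |
| 2, 0.5 | 0.046 | 0.052 | 0.030 | 0.040 |

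**What one 8:4 trial would show.** With SD 1 and a fall of 1, the expected estimate is −1 + 1/3 = −0.67 (power 0.27) if hippocampus-first is larger and −1 − 1/3 = −1.33 (power 0.92) if sham-first is larger, against −1.00 (power 0.84) with the term. With SD 1.5 and a fall of 0.5 it is −0.83 (0.38) or −1.17 (0.65), against −1.00 (0.50).

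**Precision.** The confidence interval without the term is the wider one only above a shift of about 0.14 SD at 6:6, 0.22 SD at 7:5 and 0.39 SD at 8:4. Below that it is slightly narrower, but off-centre if the split is unequal and any shift is present.

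**The case against.** The documents show no shift. Regression to the mean after the entry rule (average pain above 4/10) is plausible, but entrants have at least six months of daily pain, and the 7–10 days of ratings before round 1 may absorb much of it. App ratings run twice daily throughout, so a baseline before each round could be used, and a pure level shift would then cancel. All four scenarios use the less favourable reading of baseline.

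The gain is also modest over much of the range. Averaged over the 9:9 splits, the round term starts to gain power only at a shift of about 0.20–0.25 SD, and costs up to about 2 points at no shift. Bias averages zero over allocations, averaged type I error stays below 5%, and the raised one-sided error at 8:4 needs an imbalance in one particular direction. Pain is the secondary outcome in Study Endpoints, the study is preliminary, and it sets no power target.

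All of this stands, and it limits the size of the problem. It does not supply the missing term. The documents do not establish a baseline for each round, and the one trial that is analysed will carry whatever shift remains at its own split. That the term is standard for this design and cheap is not in dispute.

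**Conclusion.** The concern holds. The planned model omits round from a two-period crossover, and nothing else in the documents makes up for it. The main consequence is lost power: about 26 points averaged over splits if the shift is 1 SD (0.61 against 0.87), 14 points at two thirds of an SD, and 1 to 3 points at a quarter to a third of an SD. False positives are not raised on average. In a single trial with an unequal split the estimate can move either way, by a third of the shift at 8:4. These sizes rest on assumed SDs, shifts and splits and on the shift surviving baseline. This is an amendment that should be made; it does not undermine the design.

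**What to change.** In the Data Analysis Plan, replace the condition-only ANOVA with a model that has fixed effects for condition and round and a random participant effect, tested on 10 df with 12 complete pairs. The two-sample crossover t-test comparing within-person round differences between sequences is equivalent. A sequence term is optional: with complete pairs it does not change the condition estimate.

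State which baseline defines change. A baseline taken in the week before round 2 would use the same days as round 1's second-week outcome, because the washout is two weeks. Report completers per sequence. When rewriting the model, also reconcile the remaining mentions of six sequences and an M1 condition with the two-sequence description.

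The cost is one degree of freedom and no new data. If there is no shift:

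| SD | Power at 6:6, without → with | Power at 8:4, without → with | Averaged over 9:9 splits |
|---|---|---|---|
| 1 | 0.88 → 0.88 | 0.88 → 0.84 | 0.88 → 0.87 |
| 1.5 | 0.56 → 0.55 | 0.56 → 0.50 | 0.56 → 0.54 |
| 2 | – | – | 0.35 → 0.34 |

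A round term does not remove carryover.
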